8.2.10. Use of Second Study Medication Dose or Rescue Medication Postdose

The proportion of subjects who use a second dose of study medication or rescue medication at 2 to 24 hours postdose during each DB treatment period will be summarized by treatment group for the FAS1 and FAS2. The corresponding p-values from Fisher's exact test will be computed for the comparison between treatment groups.

8.2.11. Subject-Rated Treatment Satisfaction at 2 Hours Postdose

The possible values of the subject treatment satisfaction scale are: 1 = very satisfied; 2 = satisfied; 3 = somewhat satisfied; 4 = neither satisfied nor dissatisfied; 5 = somewhat dissatisfied; 6 = dissatisfied; 7 = very dissatisfied.

Subject-rated treatment satisfaction based on a 7-point scale at 2 hours postdose during each DB treatment period will be summarized by treatment group for the FAS1 and FAS2. The corresponding p-values from the Wilcoxon rank-sum test will be computed for the comparison between treatment groups.

The subject-rated treatment satisfaction score at 2 hours postdose and the baseline PPMQ-R response for the same question will be compared for the DFN-02 group only. The corresponding p-value from the Wilcoxon rank-sum test will be computed for this comparison.

The difference between the subject-rated treatment satisfaction score at 2 hours postdose and the baseline PPMQ-R response for the same question will be summarized by treatment group for the FAS1 and FAS2. The corresponding p-values from the Wilcoxon signed-rank test will be computed for the comparison between treatment groups.

Additionally, the subject-rated treatment satisfaction scores will be categorized to report "satisfied" versus "neither/dissatisfied" as well as "satisfied/neither" versus "dissatisfied". The "satisfied" category consists of scores 1-3, and the "neither/dissatisfied" category consists of scores 4-7. The "satisfied/neither" group consists of scores 1-4, and the "dissatisfied" group consists of scores 5-7. Proportions of subjects in the "satisfied" versus "neither/dissatisfied", and the "satisfied/neither" versus "dissatisfied" categories will be summarized by treatment group for the FAS1 and FAS2. The corresponding p-values from Fisher's exact test will be computed for the comparison between treatment groups.

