¹³ Screening eDiary information will be kept in the source document. It is compulsory for all the subjects to check-in the eDiary every day during the entire study period. If a subject does not check-in consistently or does not report a migraine attack in the eDiary for 2 to 3 weeks, it is recommended they should be contacted by study staff to check if the subject has technical difficulties or confirm they have not experienced a migraine.

¹⁴ Arrangements should be made by the site for a timely return of the eDiary device for subjects who screen fail.

Statistical Analysis Plan

Final V1.0

[name], Ltd.
 Protocol #DFN-02-CD-012
 INC Research #1007752

Table 2 eDiary Assessments

	Randomization	Predose Baseline	Postdose				
			10, 15, 20, 30 min	1 h	1.5 h	2 h	24 h
Migraine start and aura information, study medication, and non-study medication taken for migraine attacks dosing			As applicable ¹				
Time to meaningful pain relief			As applicable up to 2 hours postdose				
Time to pain freedom			As applicable up to 2 hours postdose				
Pain level ²		X	X	X	X	X	X
Functional disability ³		X				X	X
Presence of nausea/photophobia/phonophobia [REDACTED]		X	X	X	X	X	X
Most bothersome symptom (selected between nausea, photophobia and phonophobia) ⁴		X					
PPMQ-R	X						X
Subject treatment satisfaction (7-point scale) ⁵						X	
Abbreviations: h = hour(s); min = minutes; PPMQ-R = Patient Perception of Migraine Questionnaire-Revised							
¹ End of migraine pain, and non-study medication use may occur more than 24 hours postdose.							
² Pain levels: 0 = none; 1 = mild; 2 = moderate; 3 = severe							
³ Functional disability scale: 0 = no disability, able to function normally; 1 = performance of daily activities mildly impaired, can still do everything but with difficulty; 2 =							

Statistical Analysis Plan

Final V1.0

[name], Ltd.
Protocol #DFN-02-CD-012
INC Research #1007752

performance of daily activities moderately impaired, unable to do some things; 3 = performance of daily activities severely impaired, cannot do all or most things, bed rest may be necessary

⁴ The most bothersome symptom will be collected only if more than 1 symptom is present predose; if only 1 symptom is present, it will be considered the most bothersome.

⁵ Treatment satisfaction baseline for the migraine medication to be collected prior to randomization in the PPMQ-R.

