The change from baseline to 24 hours for each subscale score, each global item score, the total score, and the total raw score will also be analyzed using the Wilcoxon signed-rank test. Baseline scores for each subscale score, each global item score, the total score, and the total raw score will be summarized by treatment group. The total score at 24 hours postdose and the total score at baseline will be compared for the DFN-02 group only. A similar comparison for the total raw scores for the DFN-02 group will be performed. The corresponding p-value from the Wilcoxon rank-sum test will be computed for those two comparisons.

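### Three DFN-02-only before-after p-values for satisfaction are not labelled descriptive, and the between-arm test of change is misnamed at 2 hours and unstated at 24 hours

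*SAP*

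**What the plan says.** Three comparisons with baseline are confined to the active arm. In SAP 8.2.11 the 2-hour satisfaction score and the "baseline PPMQ-R response for the same question will be compared for the DFN-02 group only", and the test is fixed in the next sentence: "The corresponding p-value from the Wilcoxon rank-sum test will be computed for this comparison". In SAP 8.2.12, "The total score at 24 hours postdose and the total score at baseline will be compared for the DFN-02 group only". A like comparison follows for the total raw score, and both 24-hour comparisons again use the rank-sum test.

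The baseline is described in footnote 5 of Table 2 (SAP 3.9): "Treatment satisfaction baseline for the migraine medication to be collected prior to randomization in the PPMQ-R". Protocol 10.2.1.2 places completion of the PPMQ-R at Visit 2. Protocol 6.1 has patients on their normal migraine medication during screening, so the rating refers to usual treatment.

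The SAP also plans controlled comparisons. In 8.2.11 the 2-hour score is compared between arms: "The corresponding p-values from the Wilcoxon rank-sum test will be computed for the comparison between treatment groups". The paragraph after the DFN-02-only test takes the difference between the 2-hour score and the "baseline PPMQ-R response for the same question will be summarized by treatment group for the FAS1 and FAS2", and adds: "The corresponding p-values from the Wilcoxon signed-rank test will be computed for the comparison between treatment groups". In 8.2.12 the 24-hour scores, including total and total raw, are compared between arms by rank-sum. Change from baseline to 24 hours is then analysed by signed-rank, without saying whether the contrast is within or between arms.

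SAP 11 lists all of the comparisons with baseline as additions to the protocol. SAP 6.1.1 sets two-sided 0.05 as the default for all testing.

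**The concern.** The baseline and post-dose scores rate different things. One rates a patient's usual medication, and the other rates a blinded spray used in a single attack. The gap between them contains any drug effect, plus whatever comes from expectation, the different frame of recall and who volunteers. Placebo patients give the same two ratings, so the placebo arm measures the non-drug part directly. A DFN-02-only test does not use that control.

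These p-values sit among the secondary efficacy analyses at the default 0.05, with nothing marking them as descriptive. SAP 13.2.4 allows a within-treatment p-value to appear in a row under that treatment's statistics, so a table could show one for DFN-02 and none for placebo. The natural safeguard is the between-arm comparison of the same difference. It is planned at 2 hours with an unsuitable test, and it is not clearly planned at 24 hours.

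**Working it through.** The documents give no expected satisfaction score, SD or shift, so there is no planned figure to reproduce. The check has three parts.

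**1. The planned contrasts side by side**

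| Contrast | 2 hours (SAP 8.2.11) | 24 hours, PPMQ-R total and total raw (SAP 8.2.12) |
|---|---|---|
| DFN-02 only, post-dose vs baseline | Rank-sum | Rank-sum |
| Placebo only, post-dose vs baseline | None named | None named beside it |
| Between arms, post-dose score | Rank-sum | Rank-sum |
| Between arms, post-dose minus baseline | Planned, signed-rank named | Signed-rank on change, contrast not stated |

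**2. What each contrast tests**

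Let c be the mean shift from baseline that both arms share, and δ the extra shift due to DFN-02.

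- DFN-02-only comparison: (c + δ) against 0.
- Between-arm comparison of the difference: (c + δ) − c = δ.

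If δ = 0, the first still departs from its null whenever c ≠ 0. The second does not.

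The signed-rank test ranks one set of paired or one-sample differences. A DFN-02 patient has no partner in the placebo arm, so it cannot compare the two arms. The rank-sum test takes two independent samples, but a patient's own baseline and post-dose scores are paired. In 8.2.11, for the comparisons that involve baseline, each test is therefore attached to the design that the other one fits.

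**3. Size, by simulation with δ = 0**

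Inputs: 50 per arm (SAP 3.6) and two-sided 0.05 (SAP 6.1.1). Assumed: latent bivariate normal baseline and post-dose scores with unit variance and correlation r, and a common shift s in SD units in both arms. Scores were cut at −1.5, −0.9, −0.3, 0.3, 0.9 and 1.5 into seven categories, with 2,000 trials per setting. Entries are the percentage of trials with p < 0.05.

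| r | s | DFN-02 only, rank-sum (as written) | DFN-02 only, signed-rank | Between arms, change, rank-sum | Between arms, 2-hour score, rank-sum |
|---|---|---|---|---|---|
| 0 | 0 | 4.6 | 4.6 | 4.6 | 5.2 |
| 0 | 0.3 | 30.8 | 30.1 | 5.3 | 4.5 |
| 0 | 0.5 | 64.2 | 64.4 | 4.9 | 4.6 |
| 0 | 0.8 | 97.7 | 97.5 | 5.2 | 4.5 |
| 0.3 | 0 | 2.1 | 5.1 | 5.9 | 5.2 |
| 0.3 | 0.3 | 25.7 | 37.8 | 5.3 | 5.0 |
| 0.3 | 0.5 | 67.3 | 78.7 | 5.7 | 4.1 |
| 0.3 | 0.8 | 98.4 | 99.2 | 5.4 | 4.1 |
| 0.6 | 0 | 0.4 | 4.5 | 4.6 | 5.4 |
| 0.6 | 0.3 | 20.6 | 57.6 | 4.2 | 5.4 |
| 0.6 | 0.5 | 73.1 | 95.1 | 4.9 | 4.6 |
| 0.6 | 0.8 | 99.9 | 100.0 | 4.9 | 5.4 |

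The Monte Carlo standard error at 5% is √(0.05 × 0.95 / 2000) = 0.5 percentage points, so the between-arm columns are compatible with 5% throughout.

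A second simulation worked in scale points: latent SD 1.7, scores rounded and clipped to 1–7, r of 0 or 0.3, 800 trials per setting. A common shift of 0.5 point (0.5/1.7 = 0.29 SD) gave DFN-02-only rejection in 26.6–38.5% of trials, and 1 point (1/1.7 = 0.59 SD) gave 81.6–91.8%, over both Wilcoxon tests. The between-arm rank-sum tests stayed at 3.6–5.8%.

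The rows with s = 0 show the cost of using rank-sum on paired scores. With positive correlation it rejects too rarely, in 2.1% of trials at r = 0.3 and 0.4% at r = 0.6.

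**The case against.** A reader might infer that satisfaction relative to baseline has no placebo counterpart at all, so that a shift shared with placebo would go out as a significant DFN-02 result. The documents do not support that. In 8.2.11 the very next paragraph reports the same difference for both arms and plans a between-arm p-value. In 8.2.12 the 24-hour scores are compared between arms and baseline scores are summarized by arm. The change analysis there is not restricted to DFN-02. The secondary endpoint itself is the post-dose score (SAP 4.2), and its rank-sum comparison is between arms. Neither document says that a one-arm p-value would be presented as evidence of a DFN-02 effect.

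The rejection rates also need careful reading. They are not type I errors of the one-arm test, whose null of no difference from baseline is false once a shift is assumed. The size and direction of the shift are unknown. With only 15% of placebo patients assumed pain-free at 2 hours (SAP 3.6), placebo might be rated worse than usual medication, and the one-arm test would then count against DFN-02.

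All of this stands and narrows the point. It leaves three gaps: the one-arm p-values carry no descriptive label, the 2-hour controlled comparison names a test that cannot perform it, and the 24-hour change analysis does not state its contrast.

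**Conclusion.** The concern holds in a limited form. The three DFN-02-only p-values are uncontrolled before-after comparisons and cannot by themselves show an effect of DFN-02. A shared shift would be visible in the planned 2-hour output, but the between-arm test of that difference cannot be run as named. At 24 hours a between-arm test of change in total and total raw score is not clearly specified.

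The simulations illustrate the confounding and do not predict an error rate. With no drug effect, the DFN-02-only rank-sum test rejects in 21–31% of trials at a common shift of 0.3 SD, 64–73% at 0.5 SD and 98–100% at 0.8 SD, while between-arm rank-sum tests stay at about 4–6%. These figures rest on 50 evaluable patients per arm and on assumed shifts, correlations and score distributions. The primary endpoint and the between-arm comparisons of post-dose satisfaction scores are unaffected.

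**What to change.** Revise SAP 8.2.11 and 8.2.12, and the matching entries in SAP 11, as follows.

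1. State that any conclusion about satisfaction relative to baseline rests on the between-arm comparison of the post-dose minus baseline difference, tested by Wilcoxon rank-sum. In 8.2.11 this replaces the signed-rank test now named for that comparison.
2. In 8.2.12, specify the same between-arm comparison of change for the PPMQ-R total and total raw scores.
3. Show the within-arm comparison with baseline for DFN-02 and placebo side by side, using the signed-rank test on paired differences, and label it descriptive.

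The first two changes matter most. Adding a placebo before-after p-value without them would only add another uncontrolled result.

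The cost is a wording change and an extra placebo entry in the satisfaction tables, from data already collected. A favourable one-arm DFN-02 p-value could no longer stand alone.

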8.2.12. Subject-Rated Treatment Satisfaction at 24 Hours Postdose – PPMQ-R

The PPMQ-R consists of 29 questions that assess a subject's satisfaction with migraine medication in terms of the following subscales: efficacy (11 questions), function (4 questions), ease of use (2 questions) and cost (2 questions), as well as the degree to which side effects were tolerated (tolerability; 10 questions).

In addition, three global items measuring subject satisfaction in terms of medication effectiveness, side effects and overall satisfaction are included. Items that evaluate treatment satisfaction are scored on a seven-point Likert-type scale from 1 (very satisfied) to 7 (very dissatisfied); whereas items that evaluate tolerability of side effects (i.e. bothersomeness of side effects) are scored on a five-point Likert-type scale from 1 (not at all) to 5 (extremely). For this study, the two items that comprise the cost subscale will not be used since subjects will not pay for the study medication; therefore, 27 questions and three global items will be used.

Each subscale score and the total score will be transformed to range from 0 to 100 with higher scores indicating better satisfaction or tolerability. Scale scores are transformed to a 0 to 100 range by subtracting the lowest possible scale score, dividing by the range of the scale and multiplying by 100.² The total score consists of the average of the efficacy, function, and ease of use subscale scores.³ If a response is missing, the particular subscale or global item will be considered non-evaluable. If a subscale or global item is deemed non-evaluable, or missing, the corresponding total score will also be considered non-evaluable and assigned as missing.

The scores at 24 hours postdose for each subscale score, each global item score, the total score, and the total raw score will be summarized by treatment group for the FAS1 and FAS2. The corresponding p-values from the Wilcoxon rank-sum test will be computed for the comparison between treatment groups.

Statistical Analysis Plan

Final V1.0

[name], Ltd.
Protocol #DFN-02-CD-012
INC Research #1007752

The change from baseline to 24 hours for each subscale score, each global item score, the total score, and the total raw score will also be analyzed using the Wilcoxon signed-rank test. Baseline scores for each subscale score, each global item score, the total score, and the total raw score will be summarized by treatment group. The total score at 24 hours postdose and the total score at baseline will be compared for the DFN-02 group only. A similar comparison for the total raw scores for the DFN-02 group will be performed. The corresponding p-value from the Wilcoxon rank-sum test will be computed for those two comparisons.

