6. GENERAL ASPECTS FOR STATISTICAL ANALYSIS

6.1. GENERAL METHODS

6.1.1. Summary Statistics

In general, descriptive statistical methods will be used to summarize the data from this study. With appropriate sample sizes, hypothesis testing can be performed for the primary and secondary efficacy endpoints.

The term "treatment group" refers to the applied treatment regimen during DB1 or DB2 (DFN-02 10 mg or placebo). All data collected during the study will be included in subject data listings. All subjects entered into the database will be included in subject data listings. Unless otherwise noted, the data will be sorted first by treatment group, subject number, and then by date within each subject number.

Unless stated otherwise, the term "descriptive statistics" refers to number of subjects (n), mean, median, standard deviation, minimum, and maximum for continuous data and frequencies and percentages for categorical data.

All categorical/qualitative data will be presented using absolute frequency counts and percentages. The total number of subjects in the treatment group overall (N) in the specified population will be used as the denominator for percentage calculations, unless stated otherwise in the table shell. All percentages will be presented in parentheses with 1 decimal point, unless otherwise specified. Percentages equal to 100 will be presented as 100% and percentages will not be presented for zero frequencies.

Unless specified otherwise, all statistical testing and confidence intervals (CIs) will be 2-sided and will be performed using a significance (alpha) level of 0.05.

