 - Each subscale score and the total score will be transformed to range from 0 to 100 with higher scores indicating better satisfaction or tolerability. Scale scores are transformed to a 0 to 100 range by subtracting the lowest possible scale score, dividing by the range of the scale and multiplying by 100. The total score consists of the average of the efficacy, function, and ease of use subscale scores. If a response is missing, the particular subscale or global item will be considered non-evaluable. If a subscale or global item is deemed non-evaluable, or missing, the corresponding total score will also be considered non-evaluable.
 - The scores at 24 hours postdose for each subscale, each global item, the total score, and the total raw score will be summarized by treatment group for the FAS1 and FAS2. The corresponding p-values from the Wilcoxon rank-sum test will be computed for the comparison between treatment groups.
 - The change from baseline to 24 hours for each subscale, each global item score, the total score, and the total raw score will also be analyzed using the Wilcoxon signed-rank test. Baseline scores for each subscale score, each global item score, the total score, and the total raw score will be summarized by treatment group. The total score at 24 hours postdose and the total score at baseline will be compared for the DFN-02 group only. A similar comparison for the total raw scores for the DFN-02 group will be performed. The corresponding p-value from the Wilcoxon rank-sum test will be computed for those two comparisons.

Statistical Analysis Plan
Final V1.0

[name], Ltd.
Protocol #DFN-02-CD-012
INC Research #1007752

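### The PPMQ-R 0–100 formula in SAP 8.2.12 scores the best answers 0 and the worst 100, while the same paragraph says higher is better

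*SAP*

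**What the plan says.** SAP Section 8.2.12 makes three statements about PPMQ-R scoring.

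- **Item coding.** Satisfaction items are "scored on a seven-point Likert-type scale from 1 (very satisfied) to 7 (very dissatisfied". Items on how bothersome side effects are, which form the tolerability subscale, are "scored on a five-point Likert-type scale from 1 (not at all) to 5 (extremely". Low is good on every item.
- **Direction of the result.** Subscale and total scores run from 0 to 100, "with higher scores indicating better satisfaction or tolerability".
- **Formula.** "Scale scores are transformed to a 0 to 100 range by subtracting the lowest possible scale score, dividing by the range of the scale", with the result multiplied by 100.

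The total is the mean of the efficacy, function and ease-of-use subscale scores. SAP Section 11 repeats both the direction and the formula ("subtracting the lowest possible scale score, dividing by the range of the scale and multiplying by 100. The total score consists of the average") and adds no reversal. The protocol names the PPMQ-R at 24 hours as a secondary endpoint for each double-blind period (Section 11.4.2) but gives no scoring rule. The notes to file at the end of the SAP do not address scoring in their readable text.

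The scores are used in group summaries at baseline and at 24 hours, and in this analysis: "The change from baseline to 24 hours for each subscale score, each global item score, the total score, and the total raw score".

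**The concern.** Subtracting a constant and dividing by a positive range preserves order. If low is good before the transformation, low is good after it. The three statements can all hold only if items or scores are reversed somewhere, and no such step is written down.

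What is at stake is the sign. If the formula is coded literally and the tables are read with the SAP's direction, the more satisfied group appears less satisfied, and a subject who improves from baseline shows a fall on a scale labelled higher-is-better. This would affect all four subscales in use and the total, in DB1 and DB2. A significant p-value could then be attached to the wrong direction of effect.

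**Working it through.** **Inputs (all from SAP 8.2.12).** Item counts: "efficacy (11 questions), function (4 questions), ease of use (2 questions) and cost (2 questions", plus tolerability with 10. The cost items are not used in this study. Item limits are lo = 1 and hi = 7 for satisfaction, and lo = 1 and hi = 5 for tolerability. I take the raw subscale score as the sum of its k items; using the mean gives the same result because k cancels.

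**Formulas.**

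- As stated: T = 100 × (raw − k·lo) / (k·(hi − lo))
- Reversed: R = 100 × (k·hi − raw) / (k·(hi − lo)) = 100 − T

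**Does the plan's own description reproduce?** The 0-to-100 range does. The direction does not.

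| Subscale | k | Raw range (width) | All 1s (best): T / R | All 2s: T / R | All at maximum (worst): T / R |
|---|---|---|---|---|---|
| Efficacy | 11 | 11–77 (66) | 0 / 100 | (22−11)/66 → 16.7 / 83.3 | 100 / 0 |
| Function | 4 | 4–28 (24) | 0 / 100 | (8−4)/24 → 16.7 / 83.3 | 100 / 0 |
| Ease of use | 2 | 2–14 (12) | 0 / 100 | (4−2)/12 → 16.7 / 83.3 | 100 / 0 |
| Tolerability | 10 | 10–50 (40) | 0 / 100 | (20−10)/40 → 25 / 75 | 100 / 0 |

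**Total score.** It averages the first three rows, so all best answers give 0 as stated and 100 reversed. All 2s give 16.7 as stated and 83.3 reversed.

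**Change from baseline, efficacy.** All 4s is raw 44, which gives 33/66 = 50 under either formula. Moving to all 2s gives 16.7 − 50 = −33.3 as stated and 83.3 − 50 = +33.3 reversed. The subject has improved.

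**Recoding items first gives the same correction.** With 8 − x, an answer of 2 becomes 6, the efficacy raw score is 66, and the stated formula gives (66 − 11)/66 = 83.3. With 6 − x on tolerability, 2 becomes 4, raw is 40, and (40 − 10)/40 = 75.

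**Effect on the tests.** Since R = 100 − T, reversal turns the ranks upside down in the rank-sum test and swaps the positive and negative rank sums in the signed-rank test. Both null distributions are symmetric under this exchange, and SAP 6.1.1 says "all statistical testing and confidence intervals (CIs) will be 2-sided". The p-values are therefore identical; only the sign of differences and changes flips.

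**The case against.** The best defence is that this is an omitted step, not a contradiction. The formula acts on scale scores, which the SAP never defines as unreversed sums, and it names a total raw score separately from the total score. If items were reversed before the scale scores were formed, every sentence would hold. The intended direction is stated plainly in two places, and the cited scoring references may supply the reversal. Misreading would also be hard to miss: global items and a raw total are reported alongside, the 2-hour satisfaction item (SAP 8.2.11) has labelled categories, and SAP Section 14 requires independent programming and review by three roles. P-values do not move.

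Part of this stands. The documents do not show that anyone scored the data wrongly, so the harm is conditional. The SAP also does not say which items enter the total raw score.

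The rest does not remove the problem. The SAP writes out an explicit formula and gives the item coding just before it, with no reversal between them; followed exactly, it produces the opposite of the labelled direction. The reference attached to the formula sentence is, by its title, a heart-failure questionnaire paper. The PPMQ-R validation paper is cited only for the total. What either says about reversal cannot be settled from these documents. Two programmers working from the same formula can agree on the same inverted score, and if they disagree, the SAP does not resolve it. Unchanged p-values do not help a reader who needs to know which group was more satisfied.

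**Conclusion.** The scoring rule is wrong as written and should be corrected. Applied literally, it inverts the labelled direction of the four PPMQ-R subscales in use and of the total. The discrepancy is |100 − 2T|: nothing at the midpoint, 66.7 points for a subject answering 2 throughout the satisfaction subscales (83.3 − 16.7), and 100 points at either extreme.

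The consequence is limited to sign and interpretation of summaries and changes from baseline for one secondary endpoint, in both periods. Two-sided p-values, the primary endpoint, the sample size and the safety analyses are unaffected. The three global items are affected only if the 0–100 formula is applied to them too, which the SAP does not say.

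This rests on reading the subscale score as the sum (or mean) of items as coded in SAP 8.2.12. Whether the derivation code already reverses the items is not known from the documents.

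**What to change.** In SAP 8.2.12 and its copy in Section 11, replace the formula with 100 × (highest possible score − raw score)/range. Equivalently, state that items are recoded as 8 − x (seven-point) or 6 − x (five-point) before the existing formula is applied. Use one or the other, not both. Correcting the formula is preferable to changing the direction statement, because the intended direction is explicit in both places.

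Add a sentence saying that the total raw score and the three global items stay on the original coding, where lower is better, and stating which items the total raw score includes. Footnote the direction of each score in the PPMQ-R tables (14.2.2.19.x and 14.2.2.20.x), since they would otherwise show scores running in opposite directions. Confirm that the derivation code matches.

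The cost is wording in two places, one line of derivation code if it is not already reversed, and a table footnote. No new data are needed.

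### The PPMQ-R total score can be set to missing by items that do not enter it; if single items can be left blank, usable totals would be lost

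*SAP*

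**What the plan says.** SAP 8.2.12 lists the instrument's subscales as "efficacy (11 questions), function (4 questions), ease of use (2 questions) and cost (2 questions"), plus "the degree to which side effects were tolerated (tolerability; 10 questions"). It adds that "three global items measuring subject satisfaction in terms of medication effectiveness, side effects and overall satisfaction are included". The two cost items are dropped because subjects do not pay for study medication; "therefore, 27 questions and three global items will be used".

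Three consecutive statements in that section then govern the total score:

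- Definition: "The total score consists of the average of the efficacy, function, and ease of use subscale scores".
- Item rule: "If a response is missing, the particular subscale or global item will be considered non-evaluable".
- Total rule: "If a subscale or global item is deemed non-evaluable, or missing, the corresponding total score will also be considered non-evaluable and assigned as missing".

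SAP Section 11 lists the same rule among the additions to the protocol analysis: "If a subscale or global item is deemed non-evaluable, or missing, the corresponding total score will also be considered non-evaluable".

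The total is used in three kinds of comparison in SAP 8.2.12: between arms at 24 hours in FAS1 and FAS2, change from baseline to 24 hours, and 24 hours against baseline in the DFN-02 group alone. A total raw score is analysed alongside it, but the SAP does not say which items it contains.

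**The concern.** The definition and the total rule do not cover the same items. Tolerability and the global items cannot change the value of the total, yet the total rule names global items outright, and its unqualified reference to a subscale takes in tolerability. One blank answer among these 13 responses would then remove a total whose own components are complete.

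A total removed in this way is not recovered. The LOCF rule in SAP 8.2 covers endpoints expressed as proportions of subjects with a response, and SAP 6.3 bases analyses on non-missing values. What is at stake is the number of subjects in the total-score comparisons, in a trial planned at 50 per arm. A change score would have to survive the rule at both baseline and 24 hours.

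**Working it through.** **Step 1. Reproduce the SAP's item counts (SAP 8.2.12).**

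- Full instrument: 11 + 4 + 2 + 2 + 10 = 29 questions, as stated.
- Without cost: 29 − 2 = 27, as stated.
- With the global items: 27 + 3 = 30 responses.
- Entering the total: 11 + 4 + 2 = 17.
- Not entering the total: 10 tolerability + 3 global = 13.

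**Step 2. Set out the possible readings of the total rule.**

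- By definition, the total needs 17 responses.
- On the plain wording, it needs 17 + 13 = 30.
- On a narrower reading, in which only component subscales and the global items void the total, it needs 17 + 3 = 20.

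**Step 3. Illustrate the effect.** The documents give no item-missing rate, so let p be an assumed per-item rate, with omissions independent across items. The chance that a total is evaluable at one time point is (1 − p)^17, (1 − p)^20 or (1 − p)^30. The share of computable totals discarded is 1 − (1 − p)^3 on the narrower reading and 1 − (1 − p)^13 on the plain wording.

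| Assumed p | By definition (17) | Global items also void (20) | Plain wording (30) | Computable totals discarded: narrower / plain |
|---|---|---|---|---|
| 0.1% | 98.3% | 98.0% | 97.0% | 0.3% / 1.3% |
| 0.5% | 91.8% | 90.5% | 86.0% | 1.5% / 6.3% |
| 1% | 84.3% | 81.8% | 74.0% | 3.0% / 12.2% |
| 2% | 70.9% | 66.8% | 54.5% | 5.9% / 23.1% |

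At p = 1%: 0.99^17 = 0.843, 0.99^20 = 0.818 and 0.99^30 = 0.740.

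**Step 4. Relax independence.**

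- If the 13 non-component responses are always skipped together, by 1% of subjects and independently of the other 17, the rule discards 1% of computable totals rather than 12.2%.
- If a questionnaire is either complete or wholly absent, the readings agree and the extra loss is zero.
- If the eDiary forces every item, the extra loss is also zero.

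**The case against.** **The word corresponding.** It may limit the rule to subscales that feed the total. Tolerability, 10 of the 13 items at issue, would then not void it. This is a fair reading for subscales, and the table shows its effect. It cannot explain the global items, which are named in the rule but feed no total.

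**Strictness is not contradiction.** The definition says how the total is calculated, and the rule says when it is reported. A requirement for a complete questionnaire can be programmed and is logically compatible with the definition. That stands: the rule discards more than the definition needs, but it does not make the score incoherent.

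**No loss is shown.** The PPMQ-R is completed in the eDiary (Protocol 10.2.1.4.1), and at Visit 2 the site confirms that the patient has completed it (Protocol 10.2.1.2). Nothing in the documents shows that an item can be skipped. This also stands. A reader might infer that valid totals will be lost, or might square the one-visit figures to estimate the loss of change scores. The documents support neither. Squaring would apply the 24-hour rate to a baseline questionnaire that the site checks for completion.

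**Imbalance between arms.** A reader might infer that side-effect items would be skipped more often in one arm and so bias the comparison. No document supports this, and the tolerability scale offers a not-at-all response to patients who were not bothered.

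**Limited reach.** Each subscale and global item is also analysed separately, so the component data are still reported when the total is not.

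**Conclusion.** The concern holds in conditional form. As written in SAP 8.2.12 and Section 11, the rule can remove a PPMQ-R total for which all 17 component responses are present. For the 3 global items this follows from the explicit wording. For the 10 tolerability items it follows from the plain wording, though a narrower reading is possible.

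The size is unknown. Under an assumed 1% independent item non-response, evaluable totals at one time point fall from 84.3% to 74.0%, or to 81.8% if only the global items count. Across assumed rates of 0.1% to 2%, the plain wording discards 1.3% to 23.1% of computable totals. These figures are illustrations, not forecasts. They depend on items being skippable and on omissions being independent.

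Taken literally, the dropped cost subscale would also count as missing and void every total. That is not a tenable reading, because the SAP says the cost items are not used. It does show that the sentence needs a limit.

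This is a minor point on one summary score of a secondary endpoint. The primary analysis and the sample size are unaffected.

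**What to change.** Replace the total rule in SAP 8.2.12 and its repeat in Section 11 with wording such as: *The total score is set to missing only if the efficacy, function or ease of use subscale is non-evaluable; a missing tolerability subscale or global item affects only that subscale or item.* This also settles the status of the cost subscale.

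In the same change, list the items that make up the total raw score and state its missing-data rule on the same principle: it is missing only if one of its own items is missing. If it covers more than the 17 items, its evaluable number may differ from that of the total, so the tables should show n for each score.

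The cost is one sentence in two places, one definition and one condition in the derivation program. If no single items turn out to be missing, the change to the total rule alters no result.
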